6.3.2. Caffeine, Alcohol, and Tobacco

- Participants will abstain from ingesting caffeine- or xanthine-containing products (e.g., coffee, tea, cola drinks, and chocolate) for 24 hours prior to the start of dosing until collection of the final PK sample.
- Participants will abstain from alcohol for 24 hours prior to the start of dosing until collection of the final PK sample.

- Participants who use tobacco products will be instructed that use of nicotine-containing products (including nicotine patches) will not be permitted for 6 months prior to the screening until collection of the final PK sample.

6.3.3. Activity

Participants will abstain from strenuous exercise for 48 hours prior to each blood collection for clinical laboratory tests. Participants will remain in a sitting or semi-supine position for approximately 4 hours after dosing on Day 1 of treatment period. Participants may participate in light recreational activities during studies (e.g., watching television, reading).

6.4. Screen Failures

Screen failures are defined as participants who consent to participate in the clinical study but are not subsequently entered in the study. A minimal set of screen failure information is required to ensure transparent reporting of screen failure participants to meet the Consolidated Standards of Reporting Trials (CONSORT) publishing requirements and to respond to queries from regulatory authorities. Minimal information includes demography, screen failure details, eligibility criteria, and any serious adverse events (SAEs).

Individuals who do not meet the criteria for participation in this study (screen failure) may not be rescreened.

7. TREATMENTS

Study treatment is defined as any investigational treatment(s), marketed product(s), placebo, or medical device(s) intended to be administered to a study participant according to the study protocol.

Pyrimethamine (DARAPRIM™, Arrow Pharma Pty Ltd., Australia) will be purchased and labelled at Pharmaceutical Packaging Professionals, Australia.

Calcium folinate (Leucovorin®, Pfizer Japan Inc., Japan) will be purchased by GSK Japan, and labelled at Pharmaceutical Packaging Professionals, Australia.

7.1. Treatments Administered

Study Treatment Name:	Pyrimethamine	Calcium folinate
Dosage formulation:	Tablet	Tablet
Unit dose strength(s)/Dosage level(s):	25 mg/unit dose	5 mg/unit dose
Route of Administration:	Oral	Oral
Dosing instructions:	2 tablets will be taken on Day 1 in fasted condition with 240 mL water	3 tablets will be taken on Day 1 together with Pyrimethamine, and once a day until Day 8 (a total of 8 days). Each administration will be with 240 mL water. (See Section 7.7)
Packaging and Labeling:	Study Treatment will be provided in container. Each container will be labelled as required per country requirement.	Study Treatment will be provided in container. Each container will be labelled as required per country requirement.
Manufacturer:	Arrow Pharma Pty Ltd., Australia	Pfizer Japan Inc., Japan

7.2. Dose Modification

This is a single-dose study and dose modification will not be considered.

7.3. Method of Treatment Assignment

This is an open-label and non-randomized study which consists of two groups (Japanese and Caucasian). Subjects in each group will be assigned in accordance with the unique number (randomization schedule) generated by the Biomedical Data Sciences Department at GSK, prior to the start of the study, using validated internal software.

7.4. Blinding

This is an open-label study.

7.5. Preparation/Handling/Storage/Accountability

1. The investigator or designee must confirm appropriate temperature conditions have been maintained during transit for all study treatment received and any discrepancies are reported and resolved before use of the study treatment.

2. Only participants enrolled in the study may receive study treatment and only authorized site staff may supply or administer study treatment. All study treatments must be stored in a secure, environmentally controlled, and monitored (manual or automated) area in accordance with the labeled storage conditions with access limited to the investigator and authorized site staff.
3. The investigator, institution, or the head of the medical institution (where applicable) is responsible for study treatment accountability, reconciliation, and record maintenance (i.e., receipt, reconciliation, and final disposition records).
4. Further guidance and information for the final disposition of unused study treatment are provided in the Study Reference Manual.
 - Under normal conditions of handling and administration, study treatment is not expected to pose significant safety risks to site staff. Take adequate precautions to avoid direct eye or skin contact and the generation of aerosols or mists. In the case of unintentional occupational exposure notify the monitor, Medical Monitor and/or GSK study contact.
 - A Material Safety Data Sheet (MSDS)/equivalent document describing occupational hazards and recommended handling precautions either will be provided to the investigator, where this is required by local laws, or is available upon request from GSK.

7.6. Treatment Compliance

- When the individual dose for a participant is prepared from a bulk supply, the preparation of the dose will be confirmed by a second member of the study site staff.
- When participants are dosed at the site, they will receive study treatment directly from the investigator or designee, under medical supervision. The date and time of each dose administered in the clinic will be recorded in the source documents. The dose of study treatment and study participant identification will be confirmed at the time of dosing by a member of the study site staff other than the person administering the study treatment. Study site personnel will examine each participant's mouth to ensure that the study treatment was ingested.

7.7. Concomitant Therapy

This study includes, as a part of the study treatment, administration of calcium folinate to mitigate a potential risk of pancytopenia that has developed following administration of Pyrimethamine (Section 3.3.1).

Calcium folinate 15 mg will be coadministered with Pyrimethamine on Day 1, and will continue to be administered once a day at the same time as Day 1 until Day 8 (a total of 8 days). Details for the administration with calcium folinate are also found in SoA and Section 7.1.

Any medication or vaccine (including over-the-counter or prescription medicines, vitamins, and/or herbal supplements) that the participant is receiving at the time of enrollment or receives during the study must be recorded along with:

- reason for use
- dates of administration including start and end dates
- dosage information including dose and frequency

The Medical Monitor should be contacted if there are any questions regarding concomitant or prior therapy.

Participants must abstain from taking prescription or non-prescription drugs (including vitamins and dietary or herbal supplements) within 7 days (or 14 days if the drug is a potential enzyme inducer) or 5 half-lives (whichever is longer) before the start of study treatment until completion of the follow-up visit, unless, in the opinion of the investigator and sponsor, the medication will not interfere with the study.

7.8. Treatment after the End of the Study

Subjects will not receive any additional treatment from GSK after completion of the study because only healthy volunteers are eligible for study participation.

[figure not shown]
8. DISCONTINUATION CRITERIA

8.1. Discontinuation of Study Treatment

8.1.1. Liver Chemistry Stopping Criteria

Study treatment will be discontinued **for a participant** if liver chemistry stopping criteria are met:

Phase I Liver Chemistry Stopping Criteria – Liver Stopping Event Algorithm

Liver Safety Required Actions and Follow-up Assessments Section can be found in [Appendix 6](#).

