2. SCHEDULE OF ACTIVITIES (SOA)

	Scr	Day -1	Day 1							Day 2	Day 3	Day 4	Day 5	Day 6	Day 7	Day 8	Day 15 ⁴	Follow-up Day 22 ⁴
			Pre	0 h	1 h	2 h	4 h	6 h	12 h	24 h	48 h	72 h	96 h	120 h	144 h	168 h	336 h	504 h
Admission to Unit		X																
Informed consent	X																	
Subject demography/ Medical history	X																	
Physical examination	X	X							X	X	X	X	X	X	X			X
12-lead ECG	X		X				X		X	X	X							X
Vital signs	X		X				X		X	X	X	X	X	X	X	X	X	X
Urine drug screen	X	X																
Alcohol breath test	X	X																
CO breath test	X	X																
Serological test	X																	
Haematology, clinical chemistry and urinalysis	X	X							X			X				X	X	X
Study treatment dosing				X														
Calcium folinate dosing				X ¹					X	X	X	X	X	X	X			
PK Sampling			X		X	X	X	X	X	X	X		X		X	X	X	X
SAEs ²			←=====→															
AEs ³			←=====→															
Con Med review			←=====→															
Discharge																	X	
Outpatient Visit	X																X	X

1. Calcium folinate will be coadministered with Pyrimethamine on Day 1.
2. All SAEs will be collected from the signing of the ICF until the follow-up visit at the time points specified.
3. All AEs will be collected from the start of treatment until the follow-up visit at the time points specified.
4. Subjects will return to the unit on Day 15 (±1) and 22 (±1) for the remaining PK samples and safety assessments post dose.

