3.3.1. Risk Assessment

Potential Risk of Clinical Significance	Summary of Data/Rationale for Risk	Mitigation Strategy
Investigational Product (IP) Pyrimethamine		
Pancytopenia (hematologic effects of folate deficiency)	
The GSK safety database contains 45 case reports of pancytopenia. 24 of these are related to Pyrimethamine as the only causative agent. The rest of the cases are confounded by concomitant use of sulphonamides, since it is recommended that Pyrimethamine be given simultaneously with sulphonamides to achieve optimum effectiveness. Some cases are also confounded by antibiotics and antivirals.
 
The majority of pancytopenia cases result from insufficient folate supplementation during therapy. Substantial folate deficiency - apart from pancytopenia - may cause isolated blood dyscrasias, such as: anemia, leucopenia or thrombocytopenia and such events have also been reported.
 
This association has been known for decades and it is supported by many literature reference articles [Pajor A, 1990].
	
Subjects will be supplemented with a single daily oral dose of calcium folinate for 8 consecutive days (See the SoA for details).
 
Frequent laboratory assessments for hematologic effects (full blood counts) will be carried out during the study period, and subjects monitored for signs and symptoms of depression of haematopoiesis (e.g., leucopenia, anaemia, thrombocytopenia, etc.).

Potential Risk of Clinical Significance	Summary of Data/Rationale for Risk	Mitigation Strategy

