8.1.2. QTc Stopping Criteria

A subject that meets the bulleted criterion based on the average of triplicate electrocardiogram (ECG) readings will be withdrawn from study treatment.

- QTcF > 500 msec

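### Do the stopping rules need to say whether stopping study treatment means pyrimethamine or calcium folinate?

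*Protocol*

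**What the plan says.** Three places stop treatment, and none of the text that can be read names a product.

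- Protocol 8.1.1 (liver): "Study treatment will be discontinued for a participant if liver chemistry stopping criteria are met". The algorithm announced there may sit in a figure that could not be read for this review.
- Protocol 8.1.2 (QTc): "A subject that meets the bulleted criterion based on the average of triplicate electrocardiogram (ECG) readings will be withdrawn from study treatment".
- Protocol Appendix 6, footnote 1, uses the same term when bilirubin cannot be fractionated at once.

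The term itself appears in two senses.

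- **Broad.** Section 7 gives the definition: "Study treatment is defined as any investigational treatment(s), marketed product(s), placebo, or medical device(s) intended to be administered to a study participant". Section 7.1 gives calcium folinate its own column as a study treatment, with the instruction "3 tablets will be taken on Day 1 together with Pyrimethamine, and once a day until Day 8 (a total of 8 days". Section 7.7 is explicit: "This study includes, as a part of the study treatment, administration of calcium folinate to mitigate a potential risk of pancytopenia".
- **Narrow.** In the schedule (Protocol Section 2, repeated in SAP 10.2.1) the row "Study treatment dosing" has one mark, at 0 h on Day 1. Folinate has a separate row.

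The risk table in Protocol 3.3.1 lists the folinate course as a mitigation for pancytopenia: "Subjects will be supplemented with a single daily oral dose of calcium folinate for 8 consecutive days". The same cell adds frequent full blood counts and monitoring for signs and symptoms.

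**The concern.** Once the Day 1 dose has been swallowed, no pyrimethamine is left to withhold. Read with the Section 7 definition, a mandatory stop can then remove only folinate, the product given to protect the marrow. Read with the schedule's label, the stop removes nothing, although the reporting and monitoring steps in Appendix 6 still apply. Neither outcome looks like what a stopping rule is for.

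At stake would be consistent handling. Two participants who met the same criterion could be managed differently, one losing the rest of the folinate course and the other completing it, and the text would not say which of them was the deviation.

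A second worry concerned Appendix 6, which asks for a PK sample within 24 hours of dosing after a liver event. The first scheduled post-dose chemistry is itself at 24 h, so that request seemed impossible to meet.

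**Working it through.** **Inputs.** Times come from the SAP 10.2.1 copy of the schedule, because the columns of the protocol copy are shifted in the text used here. Hours are counted from the pyrimethamine dose.

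- Pyrimethamine: 0 h only.
- Folinate: once daily at the same clock time, Day 1 to Day 8, so 0, 24, …, 168 h. The plan's own count is reproduced: 168/24 + 1 = 8 doses.
- Post-dose chemistry: 24, 96, 168, 336, 504 h.
- Post-dose ECG: 4, 12, 24, 48, 504 h.
- Post-dose PK: 1, 2, 4, 6, 12, 24, 48, 72, 120, 168, 336, 504 h.

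**Doses a stop could reach.** For a stop at time *t*, the lower count is the number of doses strictly after *t* (that day's dose already given). The upper count is the number at or after *t*.

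| Check | Time | Folinate doses open | Pyrimethamine doses open |
|---|---|---|---|
| Chemistry | 24 h | 6–7 | 0 |
| Chemistry | 96 h | 3–4 | 0 |
| Chemistry | 168 h | 0–1 | 0 |
| Chemistry | 336 h, 504 h | 0 | 0 |
| ECG | 4 h, 12 h | 7 | 0 |
| ECG | 24 h | 6–7 | 0 |
| ECG | 48 h | 5–6 | 0 |
| ECG | 504 h | 0 | 0 |

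Checks with at least one folinate dose open: 2 or 3 of 5 for chemistry plus 4 of 5 for ECG, so 6 or 7 of 10. The arithmetic behind the concern therefore holds.

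**How far the trigger is from the population.** Exclusion criterion 1 bars ALT above 1.5 × ULN, and the liver rule starts at 3 × ULN, twice that ceiling. Exclusion criterion 3 bars QTcF above 450 msec. The QTc rule needs a triplicate average above 500 msec, at least 50 msec higher, so a single scheduled ECG cannot trigger it alone.

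**What the analysis would notice.**

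- Safety and PK populations both require at least one dose of study treatment. The two products are taken together at 0 h, so membership is the same in either sense.
- PK endpoints come from pyrimethamine concentrations only (Protocol 9.4). Folinate is not assayed.
- The sample size rests on feasibility and pyrimethamine variability (Protocol 10.1.1).
- Safety is summarised descriptively by group from what is observed. Protocol 7.6 has the date and time of each clinic dose recorded, so a shortened folinate course would be visible.
- The SAP derivation of onset time since the last dose (10.3.1.1) would shift with the sense of the term. It is a timing for individual events, and no table title in SAP Appendix 9 indicates that it is used there.

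**PK sample.** Appendix 6 does not ask for a new draw prompted by the abnormal result. Six scheduled PK draws fall at or before 24 h (1, 2, 4, 6, 12 and 24 h), and the 24 h chemistry has a PK draw at the same time. A participant on schedule already has samples inside the window.

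**The case for a change.** The strongest case for a change is that both readings are awkward and the situation can arise on schedule. Stopping also does not end exposure. With the half-life of about 107 h quoted in Protocol 5.4, and assuming simple mono-exponential decline, 2^(−24/107) ≈ 86% remains after 24 h and 2^(−96/107) ≈ 54% after 96 h. In the broad sense the rule could withdraw a mitigation while the drug is still present. The sponsor discussion required by Section 9 is itself framed in the same undefined term, and waivers are not allowed. The remedy would be cheap.

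The mismatch between the schedule row and Section 7 stands, and so does the silence of the readable stopping text on the product. The rest is weaker.

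- Section 7.2 does not support the narrow sense. It says "This is a single-dose study and dose modification will not be considered" and never uses the term *study treatment*. The narrow sense rests on one row label and its SAP copy.
- Section 3.3.1 describes the planned regimen. A stopping rule departs from the planned regimen for the person who meets it, so that alone is not a contradiction. Blood counts and symptom monitoring are listed alongside folinate. Treatment discontinuation (8.1) is separate from study withdrawal (8.2), and no visible passage ends those assessments after a treatment stop.
- For the liver rule, the unread figure may name the product, so silence is not established there.
- The decision has an owner. Section 9 requires immediate sponsor discussion of whether treatment continues, Appendix 6 requires liver events to be reported within 24 hours, and Section 7.7 sends questions on concomitant therapy to the Medical Monitor. With one centre and about 12 participants, divergent handling is possible but speculative.

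**Conclusion.** No change to the plan follows. What remains is an inconsistent label: *study treatment* covers both products in Sections 7, 7.1 and 7.7 but only pyrimethamine in the schedule row, and the readable stopping text does not say which product it reaches. The two usages are for the clinical team to reconcile as an editorial matter, and no clinical rule is proposed or preferred here.

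The size is small. At most 7 folinate doses are in question for a participant who meets a stopping criterion, falling to none after Day 8. Naming the product would alter no endpoint, population, sample size or planned summary table, and the people who would decide are already named in the protocol. The PK-sample point does not hold.

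This rests on three assumptions: the schedule times are as read from SAP 10.2.1; the liver algorithm figure contains nothing that conflicts with the surrounding text; and the sponsor contact required by Section 9 takes place when a criterion is met.

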8.1.2. QTc Stopping Criteria

A subject that meets the bulleted criterion based on the average of triplicate electrocardiogram (ECG) readings will be withdrawn from study treatment.

- QTcF > 500 msec

8.2. Withdrawal from the Study

- A participant may withdraw from the study at any time at his own request, or may be withdrawn at any time at the discretion of the investigator for safety, behavioral, compliance or administrative reasons.
- If the participant withdraws consent for disclosure of future information, the sponsor may retain and continue to use any data collected before such a withdrawal of consent.
- If a participant withdraws from the study, he may request destruction of any samples taken and not tested, and the investigator must document this in the site study records.
- Refer to the SoA for data to be collected at the time of study discontinuation and follow-up and for any further evaluations that need to be completed.

8.3. Lost to Follow-Up

A participant will be considered lost to follow-up if he repeatedly fails to return for scheduled visits and is unable to be contacted by the study site.

The following actions must be taken if a participant fails to return to the clinic for a required study visit:

- The site must attempt to contact the participant and reschedule the missed visit as soon as possible and counsel the participant on the importance of maintaining the assigned visit schedule and ascertain whether or not the participant wishes to and/or should continue in the study.
- Before a participant is deemed lost to follow-up, the investigator or designee must make every effort to regain contact with the participant (where possible, 3 telephone calls and, if necessary, a certified letter to the participant's last known mailing address or local equivalent methods). These contact attempts should be documented in the participant's medical record.
- Should the participant continue to be unreachable, he will be considered to have withdrawn from the study with a primary reason of lost to follow-up.

9. STUDY ASSESSMENTS AND PROCEDURES

- Study procedures and their timing are summarized in the SoA.
- Protocol waivers or exemptions are not allowed.
- Immediate safety concerns should be discussed with the sponsor immediately upon occurrence or awareness to determine if the participant should continue or discontinue study treatment.
- Adherence to the study design requirements, including those specified in the SoA, is essential and required for study conduct.
- All screening evaluations must be completed and reviewed to confirm that potential participants meet all eligibility criteria. The investigator will maintain a screening log to record details of all participants screened and to confirm eligibility or record reasons for screening failure, as applicable.
- Procedures conducted as part of the participant's routine clinical management (e.g., blood count) and obtained before signing of ICF may be utilized for screening or baseline purposes provided the procedure met the protocol-specified criteria and was performed within the time frame defined in the SoA.
- The maximum amount of blood collected from each participant over the duration of the study, including any extra assessments that may be required, will not exceed 500 mL.
- Repeat or unscheduled samples may be taken for safety reasons or for technical issues with the samples.

9.1. Adverse Events

The definitions of an AE or SAE can be found in [Appendix 4](#).

The investigator and any designees are responsible for detecting, documenting, and reporting events that meet the definition of an AE or SAE and remain responsible for following up AEs that are serious, considered related to the study treatment or the study, or that caused the participant to discontinue the study (see Section 8).

9.1.1. Time Period and Frequency for Collecting AE and SAE Information

- All SAEs will be collected from the signing of the ICF until the follow-up visit at the time points specified in the SoA (Section 2).
- All AEs will be collected from the start of treatment until the follow-up visit at the time points specified in the SoA (Section 2).
- Medical occurrences that begin before the start of study treatment but after obtaining informed consent will be recorded on the Medical History/Current Medical Conditions section of the case report form (CRF) not the AE section.

- All SAEs will be recorded and reported to the sponsor or designee within 24 hours, as indicated in [Appendix 4](#). The investigator will submit any updated SAE data to the sponsor within 24 hours of it being available.
- Investigators are not obligated to actively seek AEs or SAEs in former study participants. However, if the investigator learns of any SAE, including a death, at any time after a participant has been discharged from the study, and he considers the event to be reasonably related to the study treatment or study participation, the investigator must promptly notify the sponsor.
- The method of recording, evaluating, and assessing causality of AEs and SAEs and the procedures for completing and transmitting SAE reports are provided in [Appendix 4](#).

